7.5.5 Exploratory Efficacy Analyses

No adjustments for multiplicity will be done for exploratory endpoints; only nominal p-values will be presented.

7.5.5.1 Proportion of Subjects Achieving Composite Response Targets

The proportion of subjects achieving composite response targets will be summarized by treatment group without adjustment for baseline for the following composite response endpoints:

- Proportion of subjects achieving a therapeutic glycemic response, defined as HbA1c < 7.0%, without any hypoglycemia at Week 52.
- Proportion of subjects achieving a therapeutic glycemic response, defined as HbA1c < 7.0%, without any hypoglycemia and weight gain at Week 52.
- Proportion of subjects achieving a therapeutic glycemic response, defined as HbA1c < 7.0%, without any hypoglycemia at Week 156.
- Proportion of subjects achieving a therapeutic glycemic response, defined as HbA1c < 7.0%, without any hypoglycemia and weight gain at Week 156.

7.5.5.2 Mean Change from Baseline at Week *t*

The analyses of change from baseline in exploratory endpoints including HbA1c, FPG, uACR, fasting plasma glucose, body weight, and SBP at Week 52 and Week 156 (if applicable) will be performed using the longitudinal repeated measures model as described in Section 7.1.2. The analysis of change from baseline for metabolic measures (glucagon, C-peptide, pro-insulin, insulin, iHOMA2), average glucose values and post-prandial glucose values measured by 6-point SMBG profiles (ST analysis only) will be performed using ANCOVA model as described in Section 7.1.3. The statistical model assumptions will be checked, especially because uACR results are often skewed.

7.5.5.3 Change from Baseline for Lipids

The change from baseline in Triglycerides, Total Cholesterol, LDL and HDL parameters during the short-term and long-term treatment periods will be summarized for each treatment group at visits 52 and 156 only. The data will be summarized by arithmetic mean, SD, geometric means and coefficient of variation (CV), minimum, maximum, Q1, Median and Q3 values.

7.5.5.4 Mean Change from baseline in endpoints for sub-study

In the CGM sub-study, CGM will be performed for periods of 7 days at baseline and at Week 52 of treatment. Mean amplitude of glucose excursions (MAGE) for a 24-hr period is calculated in the way defined in Section 7.1.3. The average of the 7 MAGE values at baseline or at Week 52 will be used for analyses. Analyses of the mean change from baseline in MAGE at Week 52 will be performed using the ANCOVA model based on LOCF data.

In the MRI-PDFP sub-study, the mean change from baseline in visceral and subcutaneous adipose tissue volume and percent hepatic lipid content as assessed by MRI at Week 52 will be performed using the ANCOVA model based on LOCF data.

The analysis of the mean change from baseline in visceral and subcutaneous adipose tissue volume and percent hepatic lipid content as assessed by MRI at the Week 122 CRF visit will be performed using the same longitudinal repeated measures model as described in Section 7.1.2.

MRI values from an earlier visit are used instead of values at Week 52/122 for patients who are rescued or prematurely discontinued prior to Week 52/122. MRIs from week 52/122 could have been scheduled up to 4 weeks after the Rescue or Premature Treatment Discontinuation Date.

The analysis of percent hepatic lipid content will be adjusted for baseline weight.

Liver fat fraction (%) will also be summarized in a shift tables from baseline to week 52 (in the ST summary), and weeks 52 and 122 (in the ST+LT summary), using categories of $\geq 5.5\%$ and $< 5.5\%$.

For MRI laboratory data (visceral adipose tissue, subcutaneous adipose tissue and liver fat function) obtained from day 2, up to and including the last short-term double-blind dosing date + 27 days (see Table 8.4M) will be considered as obtained during the short-term double-blind treatment period. MRI laboratory data obtained from the day after the last study medication up to the last visit date of the follow-up period will be considered as obtained during the follow-up

period. MRI laboratory data obtained from the first day of long-term treatment up to including the last day of long-term medication (excluding assessments that were within 27 days from last day of ST double-blind treatment and were assigned to Week 52 analysis visit) will be considered as obtained during the combined short- and long-term treatment periods.

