7.1.2 Longitudinal Repeated Measures Analysis

A longitudinal repeated measures analysis using “direct likelihood” will be performed. The SAS procedure PROC MIXED will be used. The preferred model will include the fixed categorical effects of treatment, week, and treatment-by-week interaction as well as the continuous fixed covariates of baseline measurement and baseline measurement-by-week interaction.

The following general model will be used:

$$C_{ijk} = \text{intercept} + \beta_1 [M_{\text{baseline},ij}] + \tau_i + \alpha_k + (\alpha \tau)_{ik} + (\alpha M_{\text{baseline}})_{ijk} + \text{error}_{ijk}$$

(Model 7.1.2.1)

where:

C_{ijk} is the change from baseline for subject j in treatment group i at time k ,

β_1 is the slope coefficient for the baseline measurement,

$M_{\text{baseline},ij}$ is the baseline measurement of subject j in treatment group i ,

τ_i is the mean effect of treatment group i ,

α_k is the mean effect at time k

$(\alpha \tau)_{ik}$ is the interaction term between treatment group i and time k .

$(\alpha M_{\text{baseline}})_{ijk}$ is baseline measurement-by-week interaction term for subject j in treatment group i at time k , and

error_{ijk} is the error term for subject j in treatment group i at time k .

An unstructured matrix for the within-subject error variance-covariance will be used. The denominator degrees of freedom will be calculated according to the Kenward-Roger method.

In case of non-convergence of the preferred model or memory space issues, the following back-up models are defined:

- The first backup model is the same as the preferred model, but the Kenward-Roger method will be replaced by Satterthwaite approximation.
- The second backup model is the same as the preferred model but without the term for baseline measurement-by-week interaction.

The second back-up model will only be provided if the first back-up model does not converge or has memory issues.

If the models do not converge, then the spatial power covariance matrix will be used instead.

The model will provide least-squares mean estimates, standard errors, and 2-sided 95% confidence intervals for mean change at all time points within and between treatments.

Appropriate diagnostics will be performed to check model assumptions.

Assessment of Treatment-by-Baseline Interaction:

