7.5.3 Handling of Missing Efficacy Data

Missing data in this study may result from patients discontinuing from the study prematurely or missing intermediate visits or selected assessments while remaining on study. Every reasonable effort will be made to obtain the protocol-required data for all study assessments that are scheduled for all patients who have been enrolled.

For mixed model repeated measures (MMRM) efficacy analyses, which assumes that data are missing at random (MAR), missing observations will not be imputed.

MAR refers to missingness that is independent of missing responses, conditionally on observed responses and covariates. As the imputation strategy should always consider the dropout patterns and the time-course of the efficacy measurements by treatment, the pre- and post- withdrawal values will be assessed to understand the impact of dropouts on the efficacy results. Two additional methods of sensitivity analyses will be performed to compare the results from an MAR-based analysis versus an MNAR-based analysis under several MNAR scenarios. The first method is the return-to-baseline using Multiple Imputation in which patients with missing data known or believed to have discontinued protocol therapy were assumed to return to its baseline value and not derive any benefit from treatment. The second method is the Tipping Point Analysis, which assumes that patients from the experimental treatment arm who discontinue treatment or initiate a rescue therapy would have values worse by some amount “delta” compared to efficacy values of similar patients who continue with study treatment and do not require rescue. The detailed analysis plan and implementation of these methods are described in Section 7.5.3.1 and 7.5.3.2.

Last observation carried forward (LOCF) will also be used to handle missing data as described in Section 7.1.1.3 for analyses such as sensitivity analyses of Hb1Ac (ANCOVA) at week 52 and 156.

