8.2 Missing and Multiple Measurements

For listings of efficacy and safety measures, missing values will be represented as not reported.

If the blood pressure measurements are taken at a wrong position, e.g., sitting instead of standing, then these measurements will be excluded from the summary/analysis.

Some laboratory samples may be inadvertently analyzed multiple times for the same test, producing multiple lab results on the same collection date and time for the same subject.

In case of multiple observations within a single visit window, the following rules apply:

- If there are two or more observations within the same visit window, the non-missing observation closest to the target day will be used in the analysis
- If two observations are equidistant from the target day, the non-missing observation with the later collection date will be used in the analysis
- If two or more observations are collected on the same day and have a collection time associated with them, the non-missing observation with the later collection time will be used in the analysis
- If two or more observations are collected on the same day and time, all non-missing and the average of the observations will be used in the analysis.
- If two or more observations are collected on the same day, all non-missing but with no collection time associated with at least one of them, the average of the observations will be used in the analysis.
- For MRI visits, values from an earlier visit will be used instead of values at Week 52/122 for patients who were rescued or prematurely discontinued prior to Week 52/122. MRIs from week 52/122 could have been scheduled up to 4 weeks after the Rescue or Premature Treatment Discontinuation Date.

If a visit window does not contain any observations, the data will be missing for that visit.

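### The Week 122 MRI carry-forward rule conflicts with the SAP's no-imputation rule for repeated-measures models and, read literally, can enter one scan at two visits

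*SAP*

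**What the plan says.** SAP 7.5.5.4 uses a different method for each MRI time point. The Week 52 change "will be performed using the ANCOVA model based on LOCF data". The Week 122 change "will be performed using the same longitudinal repeated measures model as described in Section 7.1.2". The next paragraph applies one substitution rule to both: "MRI values from an earlier visit are used instead of values at Week 52/122 for patients who are rescued or prematurely discontinued". SAP 8.2 repeats it: "For MRI visits, values from an earlier visit will be used instead of values at Week 52/122 for patients who were rescued or prematurely discontinued".

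Three other provisions bear on Week 122:

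- SAP 7.5.3: "For mixed model repeated measures (MMRM) efficacy analyses, which assumes that data are missing at random (MAR), missing observations will not be imputed".
- SAP 8.2, directly after the MRI rule: "If a visit window does not contain any observations, the data will be missing for that visit".
- SAP 7.1.2: "An unstructured matrix for the within-subject error variance-covariance will be used".

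Table 8.4N makes the Week 122 window the whole long-term treatment period, ending on the last day of treatment. The Week 52 window runs 27 days past the last short-term dose. SAP 7.5.5.4 assigns MRI data from the day after the last study medication to follow-up. Protocol 5.8.6 asks subjects who are rescued or stop treatment early to attend an unscheduled scan, where possible, within 4 weeks.

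**The concern.** Carry-forward belongs with the Week 52 ANCOVA. It does not belong with a direct-likelihood model, which handles a missing Week 122 value through its correlation with the Week 52 value. If the Week 52 scan is also entered as Week 122, the model receives one scan as two post-baseline measurements, and the unstructured covariance is estimated partly from identical pairs.

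At stake are the Week 122 means and intervals for visceral fat, subcutaneous fat and liver fat. Nothing in the SAP labels the MRI rule an exception to 7.5.3, and its amendment history describes the 8.2 addition as handling of missing MRI data. Two programmers following the SAP could therefore produce different Week 122 results.

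**Working it through.** **The plan's own figures.** The documents give no SD, effect size, power, rescue rate or discontinuation rate for the MRI sub-study, only its size of about 30 per arm. The one power figure concerns HbA1c: 90% with 220 per arm, difference 0.35%, SD 1.1% and 5% non-evaluable. It reproduces (220 × 0.95 = 209 evaluable per arm, power 90.2%) but has no bearing here.

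**Which scans are affected.**

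- *Rescued during long-term treatment, scan done.* Rescued subjects stay on blinded treatment (Protocol 3.5.2), so the scan lies in the Table 8.4N window. It is a real Week 122-window value, used once.
- *Rescued, no scan done.* The only earlier value is Week 52 or older. Under 7.5.3 and the last line of 8.2, Week 122 is missing; under the MRI rule it is filled.
- *Discontinued during long-term treatment.* A scan at early termination will often follow the last dose. It then falls outside the Week 122 window and counts as follow-up, which again points back to the Week 52 scan.
- *Rescued or discontinued before Week 52.* Read literally, the rule carries a value from before Week 52 to Week 122.

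Let p be the share of subjects whose Week 52 scan is re-entered at Week 122. This is not the share rescued; p is zero if every affected subject has a scan in the window.

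**Assumed inputs.** p from 10% to 50%; Week 52–122 correlation ρ = 0.7 (also 0.4); drift from the carried scan to Week 122 of 0 or ±0.3 SD; Week 122 SD 0.8 to 1.3 times the Week 52 SD. Results are in SDs of the Week 52 change, from 4,000 simulated trials per scenario with 30 per arm.

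**Standard error of the Week 122 arm difference.** By hand, with equal SDs and no drift:

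- carried forward: √(2/30) = 0.258;
- left missing: 0.258 × √[ρ² + (1 − ρ²)/(1 − p)].

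At ρ = 0.7 the bracket is 0.49 + 0.51/0.9 = 1.057, 0.49 + 0.51/0.7 = 1.219, and 0.49 + 0.51/0.5 = 1.510. The ratio of carried-forward to left-missing SE is one over its square root.

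| p | SE, left missing (simulated) | SE, carried forward (simulated) | Ratio, simulated | Ratio, by hand |
|---|---|---|---|---|
| 10% | 0.269 | 0.259 | 0.97 | 0.97 |
| 30% | 0.291 | 0.259 | 0.89 | 0.91 |
| 50% | 0.327 | 0.259 | 0.79 | 0.81 |

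The hand formula is a large-sample one, so it gives slightly less shrinkage. Over all scenarios the simulated ratio ran from 0.71 (50%, Week 122 SD 1.3 times larger) to 1.00 (10%, Week 122 SD 0.8 times).

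**Bias.** With non-informative substitution, arm-mean bias ≈ −p × drift. For drift 0.3 SD this gives 0.03, 0.09 and 0.15 SD in size at 10%, 30% and 50%; the simulation agrees. It halves to about 0.05 SD at 30% if the carried scan lies half-way, and is about 0 without drift. In one scenario with no drift, where worse Week 52 values made rescue more likely (30%), the control mean was off by +0.06 SD.

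For the arm difference, bias ≈ −(p_T × drift_T − p_C × drift_C), where T is the combination arm and C the glimepiride arm:

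- equal rates and drift: 0;
- 20% vs 40%, drift +0.3: −(0.06 − 0.12) = +0.06 (simulated +0.06);
- 20% vs 40%, drift −0.3: −0.06 (simulated −0.05);
- 40% vs 20%, drift +0.3: −0.06 (simulated −0.06);
- drift in the control arm only: +0.09 at 30% and +0.15 at 50%.

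The model with Week 122 left missing had bias of about 0 in every scenario; all of them were missing completely at random or at random.

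**Coverage with carry-forward.** Coverage of the true Week 122 difference was 94–96% in most scenarios and 92% at worst (50%, drift in one arm only).

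**The case against.** The strongest reply is that the rule only selects among real scans. In 8.2 it sits in the list for several observations in one window, and the empty-window sentence follows it. The sentence after the rule in 7.5.5.4 refers to scans up to 4 weeks after rescue or discontinuation, which matches the unscheduled visit in the protocol. On that reading the earlier visit is the rescue or early-termination scan, and Table 8.4N already places an in-treatment scan in the Week 122 window.

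This stands for in-treatment rescue scans, whose use is window assignment and not imputation. It does not settle the rest. The unscheduled scan is requested only if possible, a scan after the last long-term dose is outside the window, and the rule carries no condition that another scan exists.

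A reader might go further and infer that the rule does bias the Week 122 mean, does understate its standard error, and that the bias cannot cancel because rescue will differ by arm. The documents do not support that. They give no rescue rate by arm or for this subset, and no expected MRI course. Bias needs drift or selective rescue. The carried-forward SE also agrees with its own sampling SD (0.259 against 0.261 at 30%); it is small only relative to the model without imputation.

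**Conclusion.** The conflict in the text is real and confined to Week 122. SAP 7.5.5.4 and 8.2 prescribe a substitution that 7.5.3 and the empty-window rule exclude, without defining the earlier visit. Where there is no scan in the window, the literal result is a Week 52 scan entered twice.

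The consequences are possible rather than established. The Week 122 mean can be biased in either direction, and the arm difference only if substitution rates or drift differ by arm. The SE reduction of about 3% to 21% rests on assumed substitution of 10% to 50%, correlation 0.7 and equal SDs; across the other assumptions tried it ran from nil to 29%. Importance is low: an exploratory sub-study of about 60 subjects with nominal p-values, outside the testing hierarchy.

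**What to change.** Amend SAP 7.5.5.4 and 8.2 as follows:

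- In the Week 122 repeated-measures model, use each eligible scan once, at the visit whose Table 8.4N window contains it. Otherwise leave Week 122 missing, as 7.5.3 states.
- Define the earlier visit as the unscheduled rescue or early-termination scan.
- Reconcile Table 8.4N with that definition by stating what post-treatment allowance, if any, applies at Week 122.
- Keep carry-forward for the Week 52 ANCOVA, or as a labelled Week 122 sensitivity analysis.

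The cost is SAP wording and a somewhat wider Week 122 interval: an SE of 0.291 against 0.259 SD in the 30% case. No new data are needed, and the primary analysis and testing hierarchy do not change.

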7.5.6 Summary of Primary Efficacy Endpoint within Subgroups

Treatment effects will be assessed for subgroups based on age group, female age group, gender, race, region, baseline HbA1c categories, and baseline eGFR categories as defined in Table 7.3.2A and Table 7.3.2B. The analyses will be based on model 7.1.2.1 with additional covariates of subgroups, treatment-by-subgroup, time-by-subgroup, and treatment-by-time-by-subgroup. The nominal p-value for subgroup-by-treatment interaction will be presented. The p-value for the test of treatment by age, female age, baseline HbA1c, and baseline eGFR interaction will include corresponding continuous subgroup variables in the model. Adjusted mean change from baseline and its difference from the control group will be given for each subgroup at week 52.

7.5.7 Pharmacokinetic Analyses

Not applicable

7.5.8 Biomarker Analyses

The change from baseline in C-Reactive protein and N-Terminal ProB-type Natriuretic Peptide parameters during the short-term and long-term treatment period will be summarized descriptively for each treatment group at week 52 and 156 only.

7.5.9 Outcomes Research Analyses

The Phase V® Health Outcomes Information System Diabetes Module will be used for the patient-reported outcomes (PRO) assessments. The self-administered PRO questionnaires consist of validated generic and diabetes-specific modules of treatment satisfaction, quality of life, barriers to medication adherence, and weight perception. Mean change from baseline in these parameters will be analyzed using longitudinal repeated measures model with terms for treatment group, baseline value, time, the interaction of treatment and time, and the interaction of baseline value and time. Point estimates and 95% confidence intervals will be calculated for the adjusted mean changes within each treatment group as well as for the differences in adjusted mean changes between treatment groups.

Phase V® is collecting the data and analyzing the data for patient reported outcomes in this study. More details on the collection and analysis is provided in Appendix 2. The outcomes research analyses will be summarized as a separate report by Phase V®.

7.5.10 Other Analysis

Not applicable.

7.5.11 Interim Analyses

There will be produced one study report at the end of Short-term Period and a second study report at the end of Short-term plus Long-term period.

7.6 Safety

The assessment of safety will be based on the analyses of AEs, vital signs, physical examinations, ECGs, hypoglycemia, and clinical laboratory evaluations. All safety analyses will be performed using treated subjects data set.

The Treated Subjects Data Set will be used for all safety analyses, including data after rescue. Safety analyses will be performed using data from the 52-week double-blind period (at the time of the primary endpoint analysis) and then again at the final database lock (156 weeks) on the combined short- and long-term treatment periods.

Additional sensitivity analyses for adverse events and laboratory marked abnormalities will be performed excluding data after rescue for the short-term double-blind treatment period. The primary analyses of events of hypoglycemia will be performed excluding data after rescue.

7.6.1 Adverse Events

Adverse events analyses will be performed for the short-term and combined short- and long-term periods.

Adverse Events (AEs) will be classified by Primary System Organ Class (SOC) and Preferred Term (PT) according to the Medical Dictionary for Regulatory Activities (MedDRA). Summaries of AEs will use the version of MedDRA that is current at the time of database lock for each study. Counting rules for adverse events are described in Section 8.8.

In summaries by SOC and PT, AEs will be sorted by international order for system organ class (SOC) and by decreasing frequency of preferred term within each SOC for Dapagliflozin + Saxagliptin + Metformin group. In summaries by PT, AEs will be sorted by decreasing frequency within PT for Dapagliflozin + Saxagliptin + Metformin group.

Separate pages to capture events of hypoglycemia are contained within the CRF. Hypoglycemia or discontinuation due to hypoglycemia would not be reported on an AE CRF page unless the event fulfilled criteria for a Serious AE (SAE) in which case an SAE form would be completed. Hypoglycemia events that are reported as SAEs will be included in all summaries of AEs or SAEs (see Section 7.6.1.1). Separate summaries will be provided including hypoglycemia events reported on that special CRF pages.

Extra details of surgical or spontaneous amputation are captured on CRF pages separate to the AE pages. Amputation AE/SAE will be included in the summaries of AE/SAEs. In addition, separate summaries will be provided including AEs leading to surgical or spontaneous amputation, an overview of adverse events leading to surgical or spontaneous/non-surgical amputations, and contributing factors and conditions that triggered any surgical or spontaneous/non-surgical amputations.

